#### Concomitant Medications

Concomitant medications are defined as prescribed medications and therapies, and over the counter (OTC) preparations, including herbal preparations and vitamins, other than Study medication taken during the study i.e., Concomitant medications are medications taken by subject on/after the start of first study-drug administration. If a medication starts before study entry and continues through the study that will be considered both as prior and concomitant.

Prior and concomitant medication will be categorized by preferred Term and ATC level X class per World Health Organization Drug Dictionary (WHODRUG; Version Global C3 2021SEP) and will be summarized by treatment group and overall, for the Safety Population. The count and percentage of patients using each medication will be displayed. Patients who taken the same medication (in terms of PT) more than once will be counted only once for that medication.

All Prior and concomitant medications will be presented in a listing for the Safety Population.

### **15.3.9 Device and Product Accountability**

Device and product accountability will be summarized using descriptive statistics such as n, mean, median, minimum, and maximum for continuous variables and count and percentages will be provided for categorical variables by treatment group and overall for the Safety Population. A listing will be provided for device and product accountability, including details about the kit dispensing for the Safety Population.

### **15.4 Subgroup Analysis**

The primary endpoint will be compared between the following pre-specified subgroups: gender, age split at the median value, race (white, non-white), etiology (ischemic, non-ischemic), prior hospitalization within 1 year (Yes/No), systolic blood pressure split at the median value, NYHA (II vs. III/IV combined), serum creatinine split at the median, serum urea nitrogen split at the median, NT-proBNP split at the median, history of diabetes (Yes/No), and history of atrial fibrillation (Yes/No). The goal of this analysis is to assess consistency of the treatment effect within subgroups using descriptive statistics by treatment group within each subgroup and the treatment-by-subgroup interaction effect on the ITT, and PP populations.

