8.7. Subgroup Analysis

The primary endpoint will be compared between treatment groups within pre-specified subgroups defined in the SAP. There will be no formal treatment comparisons within subgroups. The purpose of the analysis within subgroups is not to show statistical significance between treatments within subgroups, but to assess the consistency of treatment effect across subgroups.

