### **4. SAMPLE SIZE**

Fifty-one (51) subjects will be included and randomly assigned in a 2 to 1 ratio to receive Furoscix (n=34) or continued medical therapy (n=17) in the home setting with 30 days of follow-up. Given the exploratory nature of this study, no formal power analysis of sample size was conducted.

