#### **6.2 Secondary Objectives:**

- Inform population enrichment strategies
- Refine pivotal trial endpoints and analytical methods
- Identify operational challenges of study design
- Assess patient adherence, competence, and experience
- Familiarize staff and patients with device application and use

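### SAP 15.4 examines effect modification by five continuous baseline variables only after a median split; an exploratory continuous interaction beside the splits would be more informative if gradients are roughly linear

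*SAP*

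**What the plan says.** SAP 15.4 lists twelve subgroup factors for the primary endpoint. Seven are categorical. The other five are continuous and all are dichotomised at the trial's own median: age, systolic blood pressure ("systolic blood pressure split at the median value") and the three laboratory values ("serum creatinine split at the median, serum urea nitrogen split at the median, NT-proBNP split at the median"). The section then asks for descriptive statistics within each subgroup and for "the treatment-by-subgroup interaction effect on the ITT, and PP populations".

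The stated purpose is modest. SAP 15.4 says "The goal of this analysis is to assess consistency of the treatment effect within subgroups using descriptive statistics by treatment group". Protocol 8.7 adds "There will be no formal treatment comparisons within subgroups" and gives the aim as "to assess the consistency of treatment effect across subgroups".

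Neither document gives a clinical or prior reason for the median as the cut, and neither plans an interaction with any of the five variables left continuous. Baseline NT-proBNP does appear as a continuous covariate in the GEE model of SAP 15.2.1.1, but only as a main effect.

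One of the secondary objectives in SAP 6.2 and Protocol section 2 is "Inform population enrichment strategies". Neither document says which analysis serves it.

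**The concern.** All five values are due on every subject at Day 0 (Protocol 6.2.1 and 6.2.13), so a continuous interaction needs no new data. After a median split, a subject just above the cut counts the same as the most extreme subject. The cut also falls wherever these 51 subjects happen to put it, so a high/low contrast does not show over what range of, say, NT-proBNP the effect changes, and the cut need not carry over to a pivotal population.

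An interaction estimated from 34 against 17 subjects is imprecise to begin with. If the split adds imprecision, a real gradient is more easily read as a consistent effect. That matters because 15.4 is the only planned analysis that bears on who benefits more, in a pilot that is meant to inform enrichment.

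**Working it through.** **Inputs from the documents.** N = 51, allocated 34 and 17 (SAP 4; 51 × 2/3 = 34 and 51/3 = 17). Two-sided 0.05 and no multiplicity adjustment (SAP 15). Five modifiers cut at the median (SAP 15.4). The plan states no power or precision for any interaction, so there is no figure to reproduce.

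**Step 1: information kept by a median split.** With a linear gradient, the relative efficiency is the squared correlation between the modifier X and the indicator of X above its median. For standard normal X and a ±1 indicator, the correlation is E|X| = √(2/π) = 0.798, so the efficiency is 2/π = 0.637 and the loss is 1 − 0.637 = 36%. The variance ratio is 1/0.637 = 1.57. The split analysis of 51 subjects is worth about 51 × 0.637 = 32, and about 51 × 1.57 = 80 would be needed to recover the difference.

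**Step 2: dependence on the distribution.** Same formula, gradient linear on the scale shown:

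| Modifier | Loss |
|---|---|
| Uniform | 25% |
| Normal | 36% |
| t, 5 df | 46% |
| Lognormal, log-SD 0.5, linear in the raw value | 48% |
| Laplace | 50% |
| Lognormal, log-SD 1, linear in the raw value | 73% |

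**Step 3: power at 34 against 17.** The documents give no gradient, so a range is assumed. Model: x ~ N(0,1), y = −0.3D − b·D·x + 0.3x + N(0,1), where D is treatment. The OLS interaction test uses x either continuous or cut at the sample median, with 4,000 runs per setting. The same test was applied to the per-subject score U_i from the scoring in SAP 15.2.1, with assumed independent event rates of 3%, 12% and 12% for the three event tiers.

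| Gradient b | NT-proBNP change: continuous / split | Gain (points) | U_i: continuous / split | Gain (points) |
|---|---|---|---|---|
| 0 (null) | 4.7% / 4.9% | – | 4.8% / 4.9% | – |
| 0.3 | 15.2% / 11.7% | 3.5 | 7.3% / 6.8% | 0.5 |
| 0.5 | 35.6% / 24.3% | 11.3 | 13.1% / 9.9% | 3.2 |
| 0.7 | 57.9% / 39.9% | 18.0 | 22.2% / 15.4% | 6.8 |
| 0.9 | 80.2% / 58.8% | 21.4 | 30.4% / 21.8% | 8.6 |
| 1.1 | not run | – | 40.5% / 28.3% | 12.2 |

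Repeat runs at b = 0.5 to 0.9 on NT-proBNP change and 0.7 to 1.1 on U_i agreed to about 2 points in each cell. A separate simulation with no average treatment effect (8,000 runs) gave 35% against 25% at b = 0.5, 70% against 52% at 0.8 and 86% against 69% at 1.0, with simulated efficiencies of 0.61 to 0.66.

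**Step 4: where the split does better.** If the effect truly steps at the median, the order reverses: at a coefficient of 0.8, power was 53% continuous against 63% split.

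**Step 5: cell sizes.** A half of 25 subjects holds on average 17 × 25/51 = 8.3 controls, with a 95% range of 5 to 12.

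**The case against.** The strongest objection is that power is the wrong yardstick. Section 15.4 is descriptive, Protocol 8.7 rules out formal comparisons within subgroups, and SAP 4 calls the study exploratory and unpowered. No decision hangs on an interaction test. This stands as a limit on weight. It does not remove the point, because 15.4 still asks for an interaction effect, and the same loss appears as a wider interval.

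A reader might infer that 15.4 is the enrichment analysis and that the objective therefore fails. The documents do not support that. The link is an inference from 15.4 being the only planned analysis of effect modification by baseline.

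A reader might also infer that a third of the data is thrown away for nothing. That goes too far on three counts:

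- The fraction depends on the distribution and on linearity (steps 2 and 4).
- The split has merits: it assumes no linear form, resists outliers in skewed laboratory values and supplies the groups for the within-subgroup display.
- The raw values are kept and listed (SAP 7.1), so a continuous model can be run later, although its scale and variables would then be chosen after seeing the data.

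The assumed gradients are strong. With a main effect of −0.3, treatment is worse than control when x < −0.3/b, which is Φ(−0.6) = 27% of subjects at b = 0.5 and Φ(−0.33) = 37% at b = 0.9. For NT-proBNP change this does not alter the comparison: treatment is in the model, so the interaction test does not depend on the main effect. With a main effect of −1.0 the power is the same, and at b = 0.9 only Φ(−1.11) = 13% are reversed. That argument does not carry over exactly to U_i.

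Finally, the primary endpoint is the composite, where the gain is modest and power stays at or below about 40% by either method. A null interaction on the composite could be misread as consistency whichever analysis is used. This stands too.

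**Conclusion.** The point holds as a conditional improvement. Section 15.4 examines five continuous modifiers only through a median split. With a roughly normal modifier (log scale for the three laboratory values) and a linear gradient, the split keeps about 64% of the interaction information. The loss is about 25% to 73% under the other distributions tried, and there is none if the effect steps at the median.

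The practical gain is clearest on Day 7 NT-proBNP change: 11 to 21 points of power for gradients of 0.5 to 0.9. It is about 6 to 12 points on the composite score for gradients of 0.7 or more, and negligible for weak gradients. Gradients and tier rates are assumptions. The plan contains no contradiction or bias on this point, and the primary result does not change. Priority: optional to low.

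**What to change.** In SAP 15.4:

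- Keep the median-split tables for display and as a check on linearity, and leave the seven categorical factors as they are.
- Pre-specify an exploratory treatment-by-baseline interaction for age, systolic blood pressure, serum creatinine, serum urea nitrogen and NT-proBNP as continuous variables, with the last three on the log scale.
- Apply it mainly to Day 7 NT-proBNP change. Report the slope, its 95% CI and a plot of the estimated treatment effect over the observed range.
- As a supportive analysis, apply it to U_i divided by n − 1 (50 when n = 51), because SAP 15.2.1 bounds U_i at ±(n − 1). State that this slope is specific to this trial's size and allocation and does not transfer directly to a pivotal trial.
- Report all of these as estimates, without significance claims. Five modifiers, two outcomes and two populations give 5 × 2 × 2 = 20 estimates with no multiplicity adjustment.

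The cost is one SAP paragraph and a few model runs on data already collected. The downside is the assumption of an approximately linear gradient. With 17 controls, a few extreme values may also drive a slope; the retained splits and the plot help readers check both.
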